4.1.2 Exclusion Criteria

Participants meeting any of the following criteria will be excluded from the study:

Prior/Concomitant Therapy

1. Cohort A only: Individuals who have previously received ANY investigational or authorized MERS-CoV, SARS-CoV, and SARS-CoV-2 vaccines (including ARCT-021).
2. Cohort B only: Individuals who have the following:
 - a. Previously received BNT162b2 but have not received 2 doses within at least 5 months prior to study enrollment
 - b. Previously received another authorized or investigational vaccine (including ARCT-021)
3. Individuals receiving treatment with another investigational drug, biological agent, or device within 30 days of Screening, or 5 half-lives of investigational drug, whichever is longer; or currently enrolled in or plans to participate in another clinical study with an investigational agent during the study period.
4. Individuals who have plans to receive off-study COVID-19 vaccines during the study period.
5. Individuals who have received a live replicating vaccine within 28 days prior to first study vaccination or a licensed inactivated or non-replicating vaccine within 14 days prior to first study vaccination.

Medical Conditions

6. Individuals with significant infection or other acute illness, including body temperature of $>100.4^{\circ}\text{F}$ ($\geq 38.0^{\circ}\text{C}$) on the day prior to or on Day 1. See Section 4.2.1.
7. Individuals with a known history of COVID-19 disease or asymptomatic SARS-CoV-2 infection (For Sub-cohort A1 and Cohort B only).
8. Individuals who are pregnant or breastfeeding.
9. Individuals with a known history of anaphylaxis, urticaria, or other significant adverse reaction to the study vaccines or its excipients. Refer to the IB for list of vaccine components.
10. Individuals with a known history of anaphylaxis to other vaccines.
11. Individuals with clinically significant abnormalities in medical history or physical examination, including but not limited to, the following:

- a. Respiratory disease (e.g., chronic obstructive pulmonary disease [COPD], asthma) requiring daily medications or oxygen currently or any treatment of respiratory disease exacerbations (e.g., COPD or asthma exacerbation) warranting hospitalization or an emergency room visit or supplemental oxygen in the last 5 years.
- b. Significant cardiovascular disease (e.g., congestive heart failure, cardiomyopathy, ischemic heart disease) or history of myocarditis or pericarditis.
- c. Neurological or neurodevelopmental conditions (e.g., migraines, epilepsy, stroke, seizures in the last 3 years, encephalopathy, focal neurologic deficits, Guillain-Barré syndrome, encephalomyelitis or transverse myelitis).
- d. Significant hematologic abnormalities (e.g., sickle cell disease, beta thalassemia, coagulation disorders).
- e. Major surgery within the past 6 months.

12. Individuals with a history of chronic liver disease.

13. Individuals with a history of autoimmune disease or immunodeficiency. See [Appendix 6](#) for details.

14. Individuals using systemic corticosteroids exceeding 10 mg/day of prednisone equivalent, allergy injections, immunoglobulin, interferon, immunomodulators, cytotoxic drugs, or other similar or toxic drugs. The use of low-dose topical, ophthalmic, inhaled, and intranasal steroid preparations will be permitted.

15. Individuals who have received immunoglobulins and/or any blood or blood products within the 4 months before the first study vaccine administration or at any time during the study.

16. Individuals with a known history of or positive Screening test for HIV, hepatitis C, or chronic hepatitis B.

17. Individuals with uncontrolled hypertension (blood pressure of $>160/100$ mm Hg).

18. Individuals with cancer within 5 years prior to Screening, except for basal or squamous cell carcinoma of the skin or carcinoma in situ of the cervix that has been successfully treated.

Diagnostic Tests

Individuals with the following abnormal Screening laboratory results:

- 19. Sub-cohort A1 only: SARS-CoV-2 nucleocapsid binding antibody test results that are positive (to be performed in South Africa and the US only, given the higher rates of SARS-CoV-2 infection in these two countries)
- 20. Alanine aminotransferase (ALT), aspartate aminotransferase (AST), gamma-glutamyl transferase (GGT), total bilirubin, or alkaline phosphatase >1.5 upper limit of normal.
- 21. Hemoglobin <9.5 g/dL for females and <10.5 g/dL for males.
- 22. Platelet count $<100 \times 10^9$ /L.
- 23. Estimated glomerular filtration rate (eGFR) <50 mL/min/1.73 m² calculated by Modification to Diet in Renal Disease (MDRD) study equation.
- 24. Other clinically significant abnormal (according to the judgment of the Investigator) Screening laboratory values.
- 25. Individuals with Type 2 diabetes and Screening hemoglobin A1c $>8.0\%$.

Other Exclusions

26. Individuals who are Investigator site staff members, employees of Arcturus or the contract research organization (CRO) directly involved in the conduct of the study, or site staff members otherwise supervised by the Investigator or immediate family members of any of the previously mentioned individuals.

4.1.3 Screen Failures

Screen failures are individuals who fail to meet all inclusion criteria or who meet at least 1 of the exclusion criteria.

Rescreening will be permitted for the following circumstances:

- Expiry of the Screening Visit window without enrollment for an individual who otherwise appeared eligible for study participation
- Screening safety laboratory assessments may be repeated up to twice if the first value is inconsistent with previously documented laboratory results and subject to the review and approval of the Medical Monitor.
- Screening vital sign assessments may be repeated twice if the first value is inconsistent with previously documented vital signs

Note: A fever the day before Screening/First Visit does not result in a Screening failure, but it would result in a delay of study vaccine administration (see below).

4.2 Delaying or Discontinuing Study Treatment and Participant Withdrawal From the Study

4.2.1 Delay in Study Treatment

Body temperature must be measured and the participant asked about recent antipyretic or analgesic use prior to each administration of study vaccine.

The following events constitute criteria for delay of study vaccination and the window of delay specified forthwith:

- Acute moderate or severe infection with or without fever at the time of dosing (delay: until afebrile for 48 hours and clinically recovered according to Investigator judgment)
 - Participants with minor illness and without fever may be vaccinated if deemed appropriate according to Investigator judgment.
- Fever without signs of acute illness, defined as body temperature $\geq 38.0^{\circ}\text{C}$ (100.4°F) (delay: Until afebrile for 48 hours)
- Use of antipyretics or analgesics within 24 hours (delay: At least 24 hours).

Vaccination may be performed once these criteria are no longer met, and this will not constitute a protocol deviation.

4.2.2 Discontinuation of Study Vaccine (Participant)

4.2.2.1 Stopping Rules for Adverse Events in Individual Participants

A participant must not receive further study vaccine administrations if they experience any of the following AEs:

- Grade 3 solicited AEs (as confirmed by a blinded SRC review)
- Any anaphylactic reaction
- Severe related (possibly, probably, or definitely) unsolicited AEs
- Any clinically apparent hypersensitivity episode that is considered at least moderate in severity, is considered possibly, probably, or definitely related to study vaccine administration (as assessed by the Investigator and review of the SRC) and has the following features:
 - is not confined to the injection site
 - is immediate in onset (within ≤ 4 hours after vaccination) OR if delayed, involves more than one organ system
- Any serious adverse event (SAE) judged to be related (possibly, probably, or definitely) to study vaccine.
- Myocarditis and/or pericarditis
- Hypertensive crisis

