6.3.1.2.1 Serious Adverse Events

An SAE is defined as any event that:

- Results in death
- Is immediately life threatening
- Requires inpatient hospitalization or prolongation of existing hospitalization
- Results in persistent or significant disability/incapacity
- Is a congenital anomaly/birth defect

Important medical events that may not result in death, be life threatening, or require hospitalization may be considered SAEs when, based upon appropriate medical judgment, they may jeopardize the participant or may require medical or surgical intervention to prevent one of the outcomes listed in this definition. Examples of such medical events include allergic bronchospasm requiring intensive treatment in an emergency room or at home, blood dyscrasias or convulsions that do not result in inpatient hospitalization, or the development of drug dependency or drug abuse.

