6.3.1.2.6 Solicited Adverse Events

The term "reactogenicity" refers to selected signs and symptoms ("reactions") occurring in the hours and days following a vaccination. These signs and symptoms are collected as solicited AEs from participants by use of the Diary Cards for 7 consecutive days following each study vaccine administration.

The following solicited AEs are included in the Paper Diary:

- Solicited local AEs: Injection site erythema, injection site pain, injection site induration/swelling, and injection site tenderness

- Solicited systemic AEs: Arthralgia, chills, diarrhea, dizziness, fatigue, fever (categorized by measured body temperature), headache, myalgia, and nausea/vomiting

The occurrence of each of these solicited AEs is regarded as a study vaccine-related AE.

Also solicited from participants but not categorized as an AE is the use of antipyretics and analgesics to prevent or treat solicited AEs.

Solicited AEs are graded for severity according to scales defined in the US FDA's Center for Biologics Evaluation and Research's Guidance: Toxicity Grading Scale for Healthy Adult and Adolescent Volunteers Enrolled in Preventive Vaccine Clinical Trials ([DHHS 2007, Appendix 5](#)).

Solicited AEs may also lead to circumstances that warrant collection of the events as unsolicited AEs. This includes any solicited AE that leads to any of the following:

- A medically attended visit
- An SAE
- Discontinuation of the study vaccine
- Withdrawal from the study
- Any solicited AE that persists beyond 7 days after each study vaccine administration

Furthermore, should the site determine that the participant experienced and failed to enter a Grade 3 or Grade 4 solicited AE in the Diary then this Grade 3 or Grade 4 solicited AE should be entered as an unsolicited AE in the eCRFs.

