6.3.1.2.9 Assessment of Severity

Solicited AEs: The intensity of solicited AEs will be graded for severity as Grade 0, Grade 1 (mild), Grade 2 (moderate), Grade 3 (severe), or Grade 4 (potentially life threatening). The severity of solicited AEs will be assessed according to scales based on the US FDA toxicity grading scales for vaccine clinical studies, as shown in [Appendix 5](#).

Unsolicited AEs: The severity of unsolicited AE will be rated as mild, moderate, or severe using the following criteria:

Mild:

- These events require minimal or no treatment and do not interfere with the participant's daily activities.

OR

- An event usually transient in nature and generally not interfering with normal activities.

Moderate:

- These events result in a low level of inconvenience or concern with the therapeutic measures. Moderate events may cause some interference with normal functioning.

OR

- An AE that is sufficiently discomforting to interfere with normal activities.

Severe:

- These events interrupt a participant's usual daily activities and may require systemic drug therapy or other treatment. Severe events are usually incapacitating.

OR

- An AE that is incapacitating and prevents normal activities.

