6.7 Surveillance for SARS-CoV-2 Infection

In concert with the collection of AEs, participants will be interviewed for potential symptoms of COVID-19 disease, recent diagnosis of SARS-CoV-2 infection, and for potential exposure to COVID-19. The assessment of causality and severity for COVID-19 events will be evaluated in accordance with practices for other unsolicited adverse events.

Potential symptoms of COVID-19 disease include, at a minimum, fever or chills, cough, shortness of breath or difficulty breathing, fatigue, muscle or body aches, headache, new loss of taste or smell, sore throat, congestion or runny nose, nausea or vomiting, and diarrhea.

Exposure to COVID-19 is defined as a participant who has had close contact (within 6 feet [2 meters] for a total of 15 minutes or more) to a person with laboratory-confirmed COVID-19 (or clinically compatible illness) or to a person who has tested positive for COVID-19 (laboratory confirmed) but has not had any symptoms.

This is irrespective of whether the person with COVID-19 or the contact was wearing a mask or whether the contact was wearing respiratory personal protective equipment (PPE).

Participants should be reminded to contact the site within 24 hours if experiencing COVID-19-like symptoms or if exposed to a confirmed COVID-19 case.

Evaluation of participants with suspected COVID-19:

6. If a participant reports symptoms of potential COVID-19, an unscheduled clinic visit should occur within 48 hours
 - a. Reported symptoms include at a minimum: fever, chills, cough, shortness of breath or difficulty breathing, fatigue, muscle or body aches, headache, new loss of taste or smell, sore throat, congestion or runny nose, nausea or vomiting, and/or diarrhea.
 - b. An exception to this is if the potential symptoms of COVID-19 are observed within 7 days following study vaccination AND the Investigator determines that these symptoms are more consistent with vaccine adverse reactions and not COVID-19 symptoms.
 - c. If local policy does not allow an unscheduled in-person clinic visit, a RT-PCR or rapid antigen test may be performed and a telemedicine visit will be conducted. Alternatively the site can bring the test kit to point of care for sample collection and perform a telemedicine visit.
7. If a participant reports a potential exposure to COVID-19, an unscheduled clinic visit should be performed within 48 hours

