APPENDIX 5 TOXICITY GRADING SCALE SOLICITED ADVERSE EVENTS

Solicited Local AEs	Grade 0	Grade 1 (Mild)	Grade 2 (Moderate)	Grade 3 (Severe)	Grade 4 (Potentially Life Threatening)
Injection Site Erythema *	<2.5 cm	2.5–5 cm	5.1–10 cm	>10 cm	Emergency Room (ER) visit, hospitalization or necrosis or exfoliative dermatitis
Injection Site Induration/Swelling **	<2.5 cm	2.5–5 cm and does not interfere with activity	5.1–10 cm or interferes with activity	>10 cm or prevents daily activity	ER visit or hospitalization or necrosis
Injection Site Pain	None	No interference with activity	Some interference with daily activity or leads to use of non-narcotic pain reliever for >24 hours	Prevents daily activity or leads to use of narcotic pain reliever	ER visit or hospitalization
Injection Site Tenderness	None	Mild discomfort to touch	Discomfort with movement	Significant discomfort at rest	ER visit or hospitalization
Solicited Systemic AEs					
Fever (°C)*** (°F) ***	<38.0 <100.4	38.0–38.4 100.4–101.1	38.5–38.9 101.2–102.0	39.0–40 102.1–104	>40 >104
Nausea/vomiting	None	No interference with activity or 1–2 episodes/24 hours	Some interference with activity or >2 episodes/24 hours without seeking medical attention	Prevents daily activity or requires outpatient IV hydration	ER visit or hospitalization for hypotensive shock
Diarrhea	<2 loose stools/24 hours	2–3 loose stools or <400 g/24 hours	4–5 stools or 400–800 g/24 hours	6 or more loose or watery stools or >800 g/24 hours or requires outpatient IV hydration	ER visit or hospitalization
Headache	None	No interference with activity	Some interference with daily activity or leads to use of non-narcotic pain reliever >24 hours	Significant; prevents daily activity or leads to use of narcotic pain reliever	ER visit or hospitalization

Solicited Local AEs	Grade 0	Grade 1 (Mild)	Grade 2 (Moderate)	Grade 3 (Severe)	Grade 4 (Potentially Life Threatening)
Fatigue	None	No interference with activity	Some interference with activity	Significant; prevents daily activity	ER visit or hospitalization
Myalgia	None	No interference with activity	Some interference with activity	Significant; prevents daily activity	ER visit or hospitalization
Arthralgia, chills, dizziness	None	No interference with activity	Some interference with activity but does not require medical intervention	Prevents daily activity and requires medical intervention	ER visit or hospitalization

Abbreviation: ER=emergency room

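### The individual stopping rule names Grade 3 solicited AEs but not Grade 4, so a Diary fever above 40 °C can miss every named trigger

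*Protocol*

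**What the plan says.** Section 4.2.2.1 of the Protocol is mandatory: any listed event bars further study vaccine. The one bullet on solicited AEs reads "Grade 3 solicited AEs (as confirmed by a blinded SRC review" and goes no higher. The other six bullets cover anaphylaxis, severe related unsolicited AEs, qualifying hypersensitivity, related SAEs, myocarditis or pericarditis, and hypertensive crisis.

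The grading scale does go higher. Section 6.3.1.2.9 lists the top two grades as separate classes, "Grade 3 (severe), or Grade 4 (potentially life threatening", and Appendix 5 has its own column headed "Grade 4 (Potentially Life Threatening". Where the protocol means both grades it says so: section 6.3.1.2.6 covers a participant who "experienced and failed to enter a Grade 3 or Grade 4 solicited AE in the Diary".

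Two definitions bear on the alternative routes. Solicited AEs are vaccine-related by rule: "The occurrence of each of these solicited AEs is regarded as a study vaccine-related AE" (6.3.1.2.6). A solicited AE is also collected as an unsolicited AE only if it leads to a medically attended visit, an SAE, vaccine discontinuation or study withdrawal, lasts beyond 7 days, or was a Grade 3 or 4 event missing from the Diary.

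**The concern.** A stopping rule should bind at least as tightly on a worse event as on a milder one. As worded, this one names the severe grade and omits the grade the protocol calls potentially life threatening. Fever shows the problem most clearly, because its Grade 4 is a thermometer reading and does not require any contact with medical care. A site applying the list exactly would refer 39.5 °C to the SRC as a named stopping event but would find no entry for 40.5 °C. At stake is whether a participant who had such a fever after dose 1 is given dose 2 of the same vaccine on Day 29.

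**Working it through.** There is no plan figure to reproduce. The check compares the text of the rules with the grading scale.

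**1. Which Grade 4 events have another route?** Section 6.3.1.2.6 lists 4 local + 9 systemic = 13 solicited AEs. In Appendix 5, Grade 4 includes an ER visit or hospitalization for 12 of them and is temperature alone for 1 (fever).

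- Hospitalization is an SAE criterion ("Requires inpatient hospitalization or prolongation of existing hospitalization", section 6.3.1.2.1). Solicited AEs count as related, so the related-SAE bullet applies.
- An ER visit makes the event a medically attended AE (MAAE), so it is also collected as an unsolicited AE. The severe-related-unsolicited bullet applies if it is rated severe.
- Fever has neither route built into its definition.

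**2. Test case.** Take a fever above 40 °C that is entered in the Diary, not medically attended, resolved within 7 days and not classed as an SAE.

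| Trigger in 4.2.2.1 | 39.0–40 °C | Above 40 °C |
|---|---|---|
| Grade 3 solicited AE, SRC-confirmed | Yes | No (Grade 4) |
| Anaphylaxis | No | No |
| Severe related unsolicited AE | No | No (still solicited) |
| Qualifying hypersensitivity | No | No |
| Related SAE | No | No |
| Myocarditis or pericarditis | No | No |
| Hypertensive crisis | No | No |
| **Matched** | **1 of 7** | **0 of 7** |

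The five pausing rules in 4.2.4 (related SAE, anaphylaxis, hypersensitivity, myocarditis or pericarditis, and severe or fatal SARS-CoV-2 infection) also give 0 of 5 for the fever above 40 °C.

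**3. Routes that could still bring it under a named trigger.**

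- *Important medical event.* Section 6.3.1.2.1 allows an event to be classed as an SAE on medical judgment if "they may jeopardize the participant or may require medical or surgical intervention to prevent one of the outcomes listed in this definition". If so, the related-SAE bullets in 4.2.2.1 and 4.2.4 are met. The automatic criterion does not apply by grade alone, because it requires an immediate threat to life and Grade 4 is only a potential one.
- *COVID-19 visit.* Section 6.7 calls for an unscheduled visit for fever, which would make the event an MAAE and an unsolicited AE. It exempts symptoms within 7 days of vaccination if "the Investigator determines that these symptoms are more consistent with vaccine adverse reactions and not COVID-19 symptoms". That window is the Diary period.

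Both routes turn on judgment.

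**4. Who is exposed.** Cohort B receives one dose, so only Cohort A is affected.

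- A1 (1:1:1, n = 12): 4 + 4 + 4.
- A2 (3:1, n = 24): 18 ARCT-154 + 6 ARCT-021.
- ARCT-154: 4 + 18 = 22. ARCT-021: 4 + 6 = 10. ARCT-165: 4. Total 22 + 10 + 4 = 36.

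**5. Time available.** Diary Cards are collected on Day 8 and dose 2 is on Day 29: 29 − 8 = 21 days.

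**The case against.** The strongest reply is that this is a drafting slip with an obvious intent. A stop at the severe grade works as a threshold, and nobody would read it to release the worse grade. A fever above 40 °C also passes through the Grade 3 band, and SAP section 4.6.2 tabulates solicited AEs by grade for each day, so a fever lasting several days could have its own Grade 3 day. The intent is very likely as described. But the bullet does not say so, and the same SAP section counts a participant once, at the highest grade, when summarizing by grade.

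The second reply is that judgment governs both cases. The Grade 3 bullet itself needs SRC confirmation. Section 4.2.2.2 bars further injections once the Investigator or SRC sees additional risk, and the SRC recommends whether to proceed with second dosing in Cohort A (7.6.1). Sections 6.3.1.2.8 and 6.5 may also bring a safety-relevant Diary entry, or a clinically significant temperature found at a visit, onto the AE page. The Diary is checked on Day 4 as well as Day 8. All this stands, and it is why the practical risk is low. None of it makes Grade 4 a named trigger.

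Third, the scenario needs several conditions at once, including no other solicited AE at Grade 3. That is fair.

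Finally, the split of 12 to 1 is not perfectly clean. Erythema and induration list necrosis (and erythema also exfoliative dermatitis) as alternatives to an ER visit or hospitalization. That is correct, but it widens the literal gap.

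**Conclusion.** The point holds: the bullet is wrong as written, and the severity is low. Read literally, the less severe fever is a named stopping event and the more severe one is not. The conclusion rests on that literal reading and on a fever that is Diary-recorded, unattended, resolved within 7 days and not judged serious. It reaches the 36 planned Cohort A participants at dose 2. That is a planned number, since enrolment is approximate and withdrawn participants may be replaced. The documents give no frequency for the event and none is assumed. No estimate, table or analysis set changes.

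**What to change.** Reword the bullet in section 4.2.2.1 to *Grade 3 or higher solicited AEs*, keeping the blinded SRC confirmation. This adds two words. It needs no change to the Diary, Appendix 5, data collection or the SAP, and it puts Grade 4 events before the SRC under the same rule as Grade 3. Make the change at the next amendment, or send sites a clarification if dose 2 visits remain.
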